Recognizing the challenge that PCPs have in staying current on all of the complexities of this condition, 58 Down syndrome specialty clinics have been formed in 32 U.S. states since 1967. Yet, despite their documented impact, the 58 DS-specialty clinics, combined, only serve about 12,000 patients with DS, which is <5% of the estimated population of people with DS living in the U.S.

In 2014, the NIH published a revised research plan for DS research stating, "For individuals living with Down syndrome and their families, there is an ongoing need to study clinical and behavioral treatments and interventions". In 2008, the Centers for Disease Control and Prevention published a "Public Health Research Agenda for Down Syndrome" stating that "more research is needed to identify optimal methods of monitoring for [the comorbid] conditions. In addition, prevention strategies need to be developed for those conditions amenable to prevention". In 2011, the American Academy of Pediatrics (AAP) created DS Health Supervision Guidelines, including age-specific screening tests and procedures. For adults, consensus-based guidelines exist.

Our preliminary studies on our rules-based online intake from, which was collaboratively developed by MGH Down Syndrome Program (DSP) and MGH Laboratory of Computer Science (LCS) has shown potential for a sizeable benefit to our users, parents/caregivers and specialists. Our research will be both novel and innovative. We will offer our already created and tested online intake platform, rebranded as "Down Syndrome Clinic to You (DSC2U)," as a direct-to-public, always-available, online service yielding comprehensive, yet personalized recommendations for patients with DS who have limited access to specialty care. We want to provide game-changing care to the overwhelming majority of patients with DS who are underserved.

RESEARCH DESIGN AND METHODS

Briefly describe study design and anticipated enrollment, i.e., number of subjects to be enrolled by researchers study-wide and by Partners researchers. Provide a brief summary of the eligibility criteria (for example, age range, gender, medical condition). Include any local site restrictions, for example, "Enrollment at Partners will be limited to adults although the sponsor's protocol is open to both children and adults."

We plan to enroll 200 parents/caregivers from around the country in a two-arm randomized controlled trial (RCT) over 21 months.

Eligibility screening questions include:

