American Indian/Alaska Native	1	1	2
Asian	5	5	10
Black/African-American	13	13	26
Hawaiian/Pacific Islander	1	0	1
White	73	71	144
Multirace	3	3	6
Other race	6	5	11
Ethnicity	Male (N)	Female (N)	Total (N)
Hispanic (Latino/Latina)	16	16	32
Non-Hispanic	83	85	168

Briefly describe study procedures. Include any local site restrictions, for example, “Subjects enrolled at Partners will not participate in the pharmacokinetic portion of the study.” Describe study endpoints.

Potential eligible participants will be directed to our study recruitment website (www.downsyndromeclinictoyou.com) to complete the eligibility screening questionnaire (Appendix A). Information of frequently asked questions and answers will also be provided on our study recruitment website (Appendix B). After a questionnaire is submitted and a parent/caregiver is deemed eligible, our study personnel will send an email notification containing a unique link to our online consent form in REDCap (Appendix C). Once they have provided consent, the parent/caregiver will continue on to complete the baseline assessment. Our study personnel will then be notified by e-mail, after which we will randomize the participant 1:1 to either the Intervention or Control arm (Appendix D).

To limit chance confounding between variables that might influence guideline compliance, we will stratify randomization based on two variables (six strata) collected prior to randomization during the Baseline assessment when data are gathered only from parents (PCPs are first surveyed after their appointment with the patient who has Down syndrome):

- Travel time to primary care physician: < 30 minutes; 30–60 minutes; > 60 minutes
- Primary insurance: public (e.g., Medicaid, Medicare) or private

Given the sequence of study procedures, we will not stratify on any variables reported by the PCP. With 200 participants randomized, we expect to

achieve effective mixing of PCP characteristics that might be associated with differential guideline compliance. Moreover, by not conditioning on PCP characteristics, findings from our primary analysis will be most broadly generalizable. However, we do want to increase precision in our secondary analyses by accounting for relevant sources of variation among PCP practices. To this extent, we will collect the following variables for inclusion as covariates:

- PCP practice size: < 5 MDs; 5–9 MDs; 10+ MDs (collected in PCP Experience Survey during Post-visit Assessment 1)

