- Parent/Caregiver Experience Survey (for Secondary Outcomes) (Appendix K)
- Primary Care Provider Experience Survey (for Secondary Outcomes) (Appendix L)

Survey Implementation

The Experience Surveys (for both the parents/caregivers and PCPs) will be administered approximately 2 weeks after the PCP visit at Post-visit Assessment 1 (T1) (Figure 1). Parents/Caregivers will be invited by e-mail to complete their experience survey through REDCap. PCPs will receive their experience survey by mail, with an option to complete the survey electronically on REDCap. PCPs whose e-mails were provided by the parents/caregivers will also receive a direct invitation by e-mail to complete their survey. In order to minimize loss to follow-up, reminder e-mails will be sent 3 times about 2 weeks apart, concluding with a phone call in the eighth week by our study personnel. We certainly hope to maximize the PCP response rate, but our primary outcomes are not dependent on their responses.

Parents/Caregivers will be asked by e-mail to complete the Health Care Outcomes Survey through REDCap approximately seven months after the PCP visit at Post-visit Assessment 2 (T2) (Figure 1). In order to minimize loss to follow-up, reminder e-mails will be sent 3 times about every 2 weeks apart, concluding with a phone call in the 8th week by our study personnel.

[figure not shown]

Figure 1. Survey implementation at various points.

- **Baseline:** Health Care Outcome Survey, PedsQL 2.0 Family Impact Module and PedsQL 4.0 parent-proxy, standard Short Form 15 Generic Core Scales
- **T₀ (PCP Visit)**
- **T₁ (Post-visit Assessment 1):** PedsQL 2.0 Family Impact Module and PedsQL 4.0 parent-proxy, standard Short Form 15 Generic Core Scales, Parent/Caregiver Experience Survey, and PCP Experience Survey
- **T₂ (Post-visit Assessment 2):** Health Care Outcome Survey, PedsQL 2.0 Family Impact Module and PedsQL 4.0 parent-proxy, standard Short Form 15 Generic Core Scales

Validation Assessment

Ten percent of the respondents across both groups will be asked to validate their self-report by providing documentation of laboratory and procedural results. For example, if parents attest to thyroid checks being done for their

sons/daughters, they will be asked to send documentation of the primary outcomes (e.g. study report or physician sign off). These participants will also receive 3 reminder e-mails and a phone call every 2 weeks.

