If discrepancies are identified between parental report and source verification in more than 10% of these samples, then our team will perform a full verification of all 200 participants. Verification will be made by source documentation (e.g., sleep study reports) or verbal confirmation through telephone calls to primary care physicians.

Primary Outcomes:

We will be measuring adherence to detect improvement in: thyroid screening, celiac disease screening, sleep apnea testing, ophthalmology exams, and audiograms

- *Thyroid*: TSH should be checked annually beginning at age 1
- *Celiac disease*: if symptoms present, obtain tTG-IgA and total IgA annually
- *Sleep study*: performed by 4 years of age and, again, if symptomatic
- *Ophthalmology exam*: annually, ages 1-5; every 2 years, ages 5-13; every 3 years, ages 13-21; every 2 years, ages 21 and older
- *Audiograms*: annually up to age 21, every 2 years thereafter

The indication for 1, 2, 3, 4, or 5 evaluations for a given participant at the time of their PCP visit based on age, history, and symptoms will be collected prior to randomization as described in the "Baseline Assessment" section.

Secondary Outcomes:

We also want to determine whether the intervention improves quality of life as measured by the nationally validated PedsQL survey instruments.

Six summary scores will be derived from the two PedsQL instruments: measures of (1) psychosocial health, (2) physical health, and (3) an overall total score from the PedsQL 4.0 parent-proxy, standard Short Form 15 Generic Core Scales; and measures of (4) parental health-related quality of life, (5) family functioning, and an (6) overall total score from the PedsQL 2.0 Family Impact Module.

We will also measure the quality of experience with the intervention from parents and PCPs and identify ways that the *Caregiver Checklist* and *Primary Care Provider Plan* could best serve the needs of underserved patients with DS. For this assessment, rather than assuming we know which questions to ask to best assess their experience, we will engage our Parent/Caregiver and PCP WGs to help us pose relevant questions. Our expectation is that the assessments will ask for their level of satisfaction with the content and

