guidance offered by the *Caregiver Checklist* and *Primary Care Provider Plan*, similar to the voluntary questionnaire used in our preliminary study described above. We also anticipate including open-text responses solicited from caregivers and providers about their experience using the system.

Data Analysis Plan

Our primary analysis will compare the mean number of caregiver-reported evaluations completed within 7 months of the index PCP visit between the intervention and usual care arms. We will analyze the data using a generalized linear model assuming beta-binomial distributed counts of evaluations among those indicated with parameters estimated by maximum likelihood. We will confirm our inference using a permutation test by direct randomization of assigned treatment labels. Significant benefit will be declared if the mean number of recommended tests is greater among participants randomized to the intervention and a two-tailed p-value for the treatment comparison is less than 0.05. A significant effect of the intervention will be declared only if the permutation test concurs with inference from the beta-binomial regression as the permutation test makes no assumptions concerning the true distribution of the data. We will analyze longitudinal changes in our secondary outcome measures using a shared-baseline repeated-measures ANOVA for each of 6 quality of life outcomes derived from the two PedsQL instruments. Linear contrasts will be used to test for treatment-specific improvements over time. As a sensitivity analysis, we will also use simple two-group Wilcoxon ranksum tests to compare changes from baseline in each follow-up assessment individually. With 6 secondary outcomes, we will test each secondary outcome at alpha = 0.008 two-tailed to control for multiple comparisons.

For studies involving treatment or diagnosis, provide information about standard of care at Partners (e.g., BWH, MGH) and indicate how the study procedures differ from standard care. Provide information on available alternative treatments, procedures, or methods of diagnosis.

Not applicable

Describe how risks to subjects are minimized, for example, by using procedures which are consistent with sound research design and which do not unnecessarily expose subjects to risk or by using procedures already being performed on the subject for diagnostic or treatment purposes.

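### Six PedsQL scores are each tested at a fixed 0.008; once one contrast per score is named, Holm at family-wise 0.05 keeps the 5% bound and can only reject as many or more.

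*Combined protocol and SAP*

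**What the plan says.** The Secondary Outcomes section defines the family: "Six summary scores will be derived from the two PedsQL instruments". Three come from the Generic Core Scales and three from the Family Impact Module, and each instrument contributes an overall total. The Data Analysis Plan fits a shared-baseline repeated-measures ANOVA to each score and adds: "Linear contrasts will be used to test for treatment-specific improvements over time". Multiplicity is handled in one sentence: "With 6 secondary outcomes, we will test each secondary outcome at alpha = 0.008 two-tailed to control for multiple comparisons". The plan gives no step-down or other sequential rule, and it states no family-wise level for these outcomes.

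The Figure 1 list under Survey Implementation schedules both PedsQL instruments at baseline and at two follow-ups. The T1 entry is "PedsQL 2.0 Family Impact Module and PedsQL 4.0 parent-proxy, standard Short Form 15 Generic Core Scales, Parent/Caregiver Experience Survey, and PCP Experience Survey" and the T2 entry is "Health Care Outcome Survey, PedsQL 2.0 Family Impact Module and PedsQL 4.0 parent-proxy, standard Short Form 15 Generic Core Scales". The plan does not say which contrast, visit or combination of visits gives the p-value to be compared with 0.008. The visit-by-visit rank-sum tests are introduced with "As a sensitivity analysis, we will also use simple two-group Wilcoxon ranksum tests to compare changes from baseline in each follow-up assessment individually". They are labelled as sensitivity analyses, so I do not count them in the family.

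**The concern.** A fixed Bonferroni cut-off holds every score to the strictest threshold, even after other scores have been declared significant. Holm relaxes the threshold as rejections accumulate and needs no assumption about correlation. That matters here because each total is reported beside other scores from its own instrument. If the intervention improves several quality-of-life scores, the fixed rule may declare fewer of them significant than Holm would under the same 5% bound.

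A condition comes with this. The arithmetic behind 0.008 assumes a family of six, which means one test per score. With two follow-up visits and no contrast named, the text leaves room for two tests per score. Neither 0.008 nor Holm over six p-values would then hold the error at 5%.

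**Working it through.** **Inputs from the documents.** Per-score level 0.008 two-tailed (Data Analysis Plan); six scores (Secondary Outcomes); PedsQL at T1 and T2 (Figure 1 list); 200 participants randomised 1:1, hence 100 per arm (Research Design and Methods).

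**Assumed inputs.** The documents give no effect size, SD or correlation for the secondary outcomes. I take standardised effects d = 0.2–0.5, equal correlation of 0.3, 0.5 or 0.8 among the six test statistics, and either 100 or 80 per arm (20% loss).

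**1. The plan's own figure.** 0.05/6 = 0.00833, which is 0.008 to three decimals. The 0.05 family level is inferred from this match.

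**2. Bound under the fixed rule.** One test per score: 6 × 0.008 = 0.048. The rule is valid.

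**3. Holm thresholds, smallest p-value first.** 0.05/6 = 0.00833, 0.05/5 = 0.0100, 0.05/4 = 0.0125, 0.05/3 = 0.0167, 0.05/2 = 0.025, 0.05/1 = 0.05. All exceed 0.008, so every score with p ≤ 0.008 is also rejected by Holm. Example: for p = 0.004, 0.009, 0.012, 0.03, 0.2, 0.5 the fixed rule rejects one. Holm rejects three and stops at 0.03 > 0.0167. If the smallest p-value exceeds 0.00833, neither rule rejects anything.

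**4. Fixed-rule power in closed form.** Power ≈ Φ(d√(n/2) − 2.652), where 2.652 is the normal quantile for 0.004 in each tail. For d = 0.4 and n = 100: 0.4 × √50 = 2.828, and Φ(0.176) = 57.0%.

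**5. Holm against fixed 0.008 by simulation.** 200,000 draws per setting, six correlated normal statistics with mean d√(n/2) for affected scores. At 100 per arm, correlation 0.5, all six scores improving:

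| d | Power per score, fixed 0.008 | Power per score, Holm 0.05 |
|---|---|---|
| 0.2 | 10.8% | 13.4% |
| 0.3 | 29.7% | 36.9% |
| 0.4 | 57.1% | 68.0% |
| 0.5 | 81.2% | 89.8% |

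Gains by number of scores that truly improve (from unrounded values):

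| Scores improving | Gain, n = 100, correlation 0.5 (points) | Trials in which the count of significant scores changes | Gain over the whole grid (points) |
|---|---|---|---|
| One | 0.3–0.6 | 0.9–1.4% | 0.3–0.6 |
| Three | 0.9–3.4 | 3.2–11.0% | 0.6–3.6 |
| Six | 2.5–10.9 | 10.2–42.8% | 1.3–11.6 |

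No fixed-rule rejection was missed by Holm in any draw. The chance of at least one significant score rises by at most 0.7 points. With six scores at d = 0.4 it goes from 90.0% to 90.3%, while the expected number of significant scores goes from 3.42 to 4.08.

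**6. Is the gain only rounding?** With one affected score, essentially yes: at d = 0.4, power is 57.0% at 0.008, 57.5% at 0.05/6 and 57.6% with Holm. With six, no: Holm run at 0.048, the fixed rule's exact bound, still gives about 67.2% against 57.0%.

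**7. What Holm gives up (n = 100, correlation 0.5).** With no true effect, family-wise error is 4.0% (fixed) and 4.2% (Holm). Expected false rejections rise from 0.048 to about 0.055. A single null score beside five true effects is falsely rejected 0.8% of the time under the fixed rule and 1.5–3.5% under Holm.

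**8. If T1 and T2 were both tested at 0.008.** The bound becomes 12 × 0.008 = 0.096. With no true effect, simulated family-wise error is 7.4% (correlation 0.5 between scores and between visits). It ranges over 4.7–8.6% for correlations of 0.3–0.8 between scores and 0.3–0.7 between visits. Holm over six, using the smaller p-value per score, gives 4.9–8.9%. Holm over twelve gives 2.6–4.6%.

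**The case against.** The strongest reply is that this is a choice between two valid procedures. The fixed rule is pre-specified, caps each score's false-positive rate at 0.8%, and comes with a simple matching 99.2% interval. Preferring that protection for secondary outcomes is reasonable. This stands, and it is why the point is only a suggested improvement.

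A second objection is that the larger gains need all six scores to improve by 0.3 SD or more. Nothing in the documents supports that for an intervention aimed at completing screening tests. At d = 0.1 (100 per arm, correlation 0.5) the gain is about 0.5 points with six scores affected, 0.2 with three and 0.1 with one. This also stands: the upper end is a favourable scenario. Equal correlation is a simplification too. Building the totals as averages of their components hardly moved the power gains, but at d = 0.4 with six affected it lowered the share of trials with a changed count from about 43% to 36–41%.

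Third, the 9.6% is conditional. The multiplicity sentence reads most naturally as one test per outcome, and the plural in "Linear contrasts will be used to test for treatment-specific improvements over time" may simply reflect six models. I agree that the plan does not say both visits are tested at 0.008, so the figure shows why the contrast should be named and is not evidence of an inflated error rate. Naming the contrast is also separate from Holm, which would not cure a twelve-test family.

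None of this alters the ordering: within the 5% bound, Holm never rejects less.

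**Conclusion.** The point holds, as a low-cost improvement and not as an error. With one test per score the fixed 0.008 controls family-wise error (at most 4.8%), but Holm at 0.05 is at least as powerful in every case. The benefit is negligible if one score improves, modest if three do, and up to about 11 points per score if all six do, at the assumed effects and correlations. In most simulated trials the number of significant scores is the same under both rules. The 0.05 family level is inferred, and the effect sizes and correlations are mine. The ordering of the two rules and the 5% bound do not depend on those effects and correlations. They do depend on each score having a single named test, which the current text does not provide.

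**What to change.** In the Data Analysis Plan, before any unblinded comparison:

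1. Name the single between-arm contrast from the repeated-measures model that supplies each score's p-value. Which visit or combination of visits it uses is the sponsor's choice.
2. Replace the fixed 0.008 with Holm at two-tailed family-wise 0.05 across the six p-values: smallest against 0.05/6, next against 0.05/5, and so on to 0.05/1, stopping at the first that fails.
3. If T1 and T2 are both to be tested for every score, state that the family is twelve and start at 0.05/12.

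The cost is one or two sentences, with no new data and no change in sample size. Simultaneous confidence intervals become less simple than the 99.2% interval that matches the fixed rule. The 0.8% per-score cap and the 0.048 cap on expected false rejections are also given up, although family-wise error stays within 5%. A sponsor who values those properties more can keep 0.008, but should still make the first change.
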